#### 2.4.4 Analyses of efficacy endpoints

For statistics where international and conventional units do not impact the results (e.g., means and least square (LS) means for percent changes from baseline, p-values for both percent and absolute changes from baseline, rates of patients below a threshold), derivations will be performed and statistical models will be run using conventional units. For other statistics (e.g., descriptive statistics at baseline and over time, absolute changes from baseline), derivations will be done with both international and conventional units.

All the efficacy endpoints (primary, key secondary and other efficacy endpoints) will be analyzed in the ITT population for the overall comparison (alirocumab versus usual care) and for patients intended to receive fenofibrate in order to compare the efficacy of alirocumab versus fenofibrate. However no subgroup analysis will be performed in the fenofibrate stratum.

# 2.4.4.1 Analysis of primary efficacy endpoint

## 2.4.4.1.1 Primary efficacy analysis

The percent change in non-HDL-C from baseline to Week 24 as defined in Section 2.1.3.1 will be analyzed in the ITT population using a mixed effect model with repeated measures (MMRM) approach. All post-baseline data available within Week 8 to Week 24 analysis windows will be used and missing data are accounted for by the MMRM model.

Let  $\mu 0$  and  $\mu 1$  be the population means of the percent change from baseline in non-HDL-C at Week 24 under usual care and alirocumab, respectively. The null hypothesis that will be tested is:

"H0: 
$$\mu$$
0 =  $\mu$ 1" versus "H1:  $\mu$ 0  $\neq \mu$ 1".

The MMRM model relies on the "missing-at-random" (MAR) assumption. As we can never exclude the possibility for a not-missing-at-random (NMAR) missingness mechanism, sensitivity analysis to explore the impact of non-ignorable missingness on the primary efficacy analysis will be conducted (see pattern mixture model defined in Section 2.4.4.1.3).

# Overall analysis

The model will include the fixed categorical effects of treatment group (alirocumab versus usual care), randomization stratum as per IVRS, time point (Week 8, Week 12, Week 20 and Week 24), treatment group-by-time point interaction, stratum-by-time point interaction, as well as the continuous fixed covariates of baseline non-HDL-C value and baseline value-by-time point interaction. In case of non-convergence of the model, a model with less interactions terms will be explored.

This model will be run using SAS® MIXED procedure with an unstructured correlation matrix to model the within-patient errors. Parameters will be estimated using restricted maximum likelihood method with the Newton-Raphson algorithm. Denominator degrees of freedom will be estimated using Satterthwaite's approximation. This model will provide baseline adjusted LS means estimates at Week 24 for both treatment groups with their corresponding standard errors (SEs). To compare the alirocumab group to the usual care group, an appropriate contrast statement will be used to test the differences of these estimates, at the 2-sided 0.025 level. LS-mean difference versus usual care and the corresponding 97.5% confidence intervals (CIs) will be provided.

# Analysis in the fenofibrate stratum

A MMRM model will also be used to compare alirocumab versus fenofibrate with additional interactions terms: treatment group-by-stratum- and treatment group-by-stratum-by-visit. The model will be run with all patients, whatever their stratum and will be also used to derive the treatment effect in the other strata (Section 2.4.4.5). In case of non-convergence of the model with the triple interaction, the same model as the primary efficacy analysis will be run in the "intent to prescribe fenofibrate" stratum.

26-Apr-2017

The appropriate contrast statement will be used to test the difference between the estimate of alirocumab group and the estimate of usual care group in the fenofibrate stratum.

## 2.4.4.1.2 Model assumption checks

The following analyses will be performed to check the model assumptions.

Homogeneity of treatment effect across baseline non-HDL-C levels:

In order to check the homogeneity of treatment effect versus baseline non-HDL-C, the following interaction terms will be added in the primary MMRM model:

- Treatment group \* baseline non-HDL-C
- Treatment group \* time-point \* baseline non-HDL-C

Within the framework of this model with interaction terms, a graph presenting the LS means difference versus usual care at Week 24 and the corresponding 97.5% CI will be provided by baseline non-HDL-C value.

Analysis of residuals:

The analysis of the residuals of the MMRM will be primarily based on studentized residuals. It will include:

- Normality of studentized residuals, presented graphically using histogram and quantile quantile (QQ)-plot
- Plot of studentized residuals versus predicted values

#### 2.4.4.1.3 Sensitivity analyses

On top of standard tables, forest plots will also be provided to present the results of the sensitivity analyses together with the main analysis.

Sensitivity to treatment change

A sensitivity analysis will be performed on the primary efficacy analysis excluding non-HDL-C values assessed after the first treatment change from the analyzed data. This analysis will be done as per analysis described in Section 2.4.4.1.1.

A treatment change is defined as:

- For alirocumab: permanent discontinuation
- For usual care: permanent discontinuation of the LMT initiated at randomization
- For both groups: add-on of a new LMT

Note: changes in dosage will not be considered in this analysis.

## Sensitivity to randomization strata

In order to assess the robustness of the primary analysis to randomization stratum mistakes (i.e., the stratum recorded in IVRS differs from the actual one), the MMRM model will be re-run including the actual stratum as per the e-CRF instead of the stratum recorded in IVRS. The actual stratum as per the e-CRF is defined, for the patients randomized to usual care only, as the actual usual care treatment taken for the longer time. In case no additional LMT is recorded using e-CRF page "Usual Care Medication for Lipid Modification therapy", the actual stratum will be assigned to "no intent to prescribe an additional LMT".

Sensitivity to handling of missing data - Pattern mixture model

In order to assess the robustness of the primary efficacy analysis with regards to handling of missing data, a sensitivity analysis will be conducted based on a pattern-mixture model approach.

Multiple imputation will be used with different imputation strategies applied to non-HDL-C values missing during the on-treatment period (as defined below)

- Patients randomized to alirocumab would continue to show benefit from treatment similar to that observed at the scheduled time point within 21 days of their last dose of open-label alirocumab (on-treatment period). Therefore, non-HDL-C values missing during the ontreatment period (e.g., samples obtained outside the specified window, no blood sample available although visit was performed, etc) should be considered as "Missing At Random" and imputed using a model based on other on-treatment measurements, gender, age and BMI;
- Patients randomized to usual care with additional LMT would continue to show benefit from treatment similar to that observed at the scheduled time point within 3 days of their last dose of LMT. Therefore, non-HDL-C values missing during the on-treatment period (e.g., samples obtained outside the specified window, no blood sample available although visit was performed, etc) should be considered as "Missing At Random" and imputed using a model based on other on-treatment measurements, gender, age and BMI;
- Patients, randomized to usual care and for whom the Investigator has not prescribed an additional LMT, would tend to have non-HDL-C values similar to baseline. Therefore, non-HDL-C values missing after randomization should be imputed based on patient's own baseline value;
- Patients who stopped taking their study treatment no longer benefited from it after discontinuation, and thus tended to have non-HDL-C values returning to baseline. Therefore, non-HDL-C values missing after on-treatment period should be imputed based on patient's own baseline value.

Missing non-HDL-C values will be imputed 100 times to generate 100 complete data sets. The percent change from baseline to Week 24 will be derived from observed and imputed non-HDL-C at this time point. The completed data sets will be analyzed using an ANCOVA model with treatment group and randomization stratum as per IVRS as fixed effects, and the baseline non-HDL-C value as continuous covariate. The results from the 100 analyses will be combined using Rubin's formulae (6).

26-Apr-2017

To assess the homogeneity of the treatment effect across various subgroups, treatment group-by-subgroup factor, time point-by-subgroup factor, and treatment goup-by-time point-by subgroup factor interaction terms and a subgroup factor term will be added as fixed factors in the primary MMRM model described in Section 2.4.4.1.1. LS means difference versus usual care at Week 24 will be provided, as well as the corresponding SE and 97.5% CI, within each subgroup. The

significance level of the treatment group-by-subgroup factor interaction term at Week 24 will be also provided for each factor for descriptive purpose. Forest plots will be provided.

For each subgroup analysis, subgroups will be included in the analysis only if there are ≥10

patients by subgroup and treatment arm. Otherwise, unless specified below, the subgroups not meeting the required number of patients will be pooled to form larger subgroups if possible, or they will be excluded from analysis.

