# 1 OVERVIEW AND INVESTIGATIONAL PLAN

### 1.1 STUDY DESIGN AND RANDOMIZATION

This is a multicenter, multinational, randomized, open-label, parallel group stratified study.

After a screening phase of up to 3 weeks, patients will be centrally randomized via interactive voice response system (IVRS) or interactive web response system (IWRS) in a 2:1 ratio to one of the two treatment groups (alirocumab:usual care) and treated for 24 weeks.

Randomization will be stratified by the Investigator's selection of usual care therapy prior to randomization (5 strata: no additional lipid modifying therapy [LMT], or intent to prescribe fenofibrate, ezetimibe, omega-3 fatty acids, or nicotinic acid). Patients randomized to open-label alirocumab will continue on the maximum dose of statin that is tolerated by the patient and will administer alirocumab subcutaneously with a starting dose of 75 mg every 2 weeks for 12 weeks with a blinded up-titration to alirocumab 150 mg every 2 weeks at Week 12 visit if the non-high-density lipoprotein cholesterol (non-HDL-C) at the Week 8 visit is ≥100 mg/dL (2.59 mmol/L). Patients who have a non-HDL-C <100 mg/dL (2.59 mmol/L) at the Week 8 visit will continue with alirocumab 75 mg every 2 weeks until the end of the treatment period. Patients randomized to usual care will follow the option selected by the Investigator prior to randomization. No change during the course of the study will be made to the dose of LMT administered as part of the usual care arm except for nicotinic acid for which the Investigator may prescribe at randomization a scheduled/gradual dose titration in order to allow for the maximum dose to be achieved based on patient tolerability, or except if needed for any usual care LMT for the safety of the patient, based on the Investigator's judgment.

Approximately 420 patients will be recruited and randomized (280 in the alirocumab group and 140 in the usual care group).

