#### 1.4 STUDY PLAN

This is a Phase 3b/4 randomized, open-label, parallel group study to assess the efficacy and safety of alirocumab administered by subcutaneous injection versus usual care in patients with Type 2 diabetes and mixed dyslipidemia at high CV risk with non-HDL-C not adequately controlled with maximally tolerated statin therapy. The study will be multinational and multicenter. The study consists of a screening period of up to 3 weeks, an open-label treatment period (OLTP) of 24 weeks, and a safety observation period of 8 weeks.

Patients, unless they are statin intolerant, will be taking a stable, maximally tolerated dose of statin therapy without other LMTs. Statin dose and dose regimen should be stable throughout the entire study duration including for 4 weeks prior to the screening period and from screening to the end of the OLTP. Patients should continue to follow a cholesterol lowering diet during the study, however, the Investigator may reinforce diet recommendations according to local/regional guidelines. Patients should be receiving treatment for diabetes in accordance with local/regional standards of care. Changes to antihyperglycemics should be limited and made only in circumstances where it is clinically needed.

The usual care arm includes the option to continue on the maximum dose of statin that is tolerated by the patient without the addition of a new LMT at randomization, or may initiate either ezetimibe, fenofibrate, omega-3 fatty acids, or nicotinic acid at randomization for the remainder of the 24-week treatment period. Initiation of usual care treatment should start as soon as possible after randomization, but no later than 7 days from the day of randomization.

The Investigator will select the most appropriate LMT for the patient prior to randomization (consisting of either no additional LMT but continuing on maximum tolerated statin, ezetimibe, fenofibrate, omega-3 fatty acids or nicotinic acid) and enter this information into the IVRS. If the patient is randomized to open-label alirocumab, the Investigator will not institute the LMT option that was selected and entered into IVRS but instead treat the patient with open-label alirocumab. If the patient is randomized to usual care (non-alirocumab), the Investigator will initiate treatment with the LMT option that was selected and entered into IVRS, as applicable, in addition to continuing the patient on the maximum tolerated dose of statin.

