#### 2.2 DISPOSITION OF PATIENTS

This section describes patient disposition for both patient study status and the patient analysis populations.

Screened patients are defined as any patients who signed the informed consent.

Randomized patients consist of all screened patients who are recorded in the IVRS/IWRS database (if randomized to usual care) and with a treatment kit allocated (if randomized to alirocumab), regardless of whether the treatment kit was used or not. Patients treated without being randomized or treated with a treatment kit before the randomization will not be considered as randomized and will not be included in any analysis population. The safety experience of patients treated and not randomized will be reported separately and these patients will not be in the safety population.

For any patient randomized more than once, only the data associated with the first randomization will be used in any analysis population. The safety experience associated with any later randomization will be assessed separately.

For patient study status, the total number of patients in each of the following categories will be presented by randomization stratum (for strata with at least 10% of patients) and in the pooled data in the clinical study report using a flowchart diagram or summary table:

Property of the Sanofi Group - strictly confidential

- Version number: Final
- Screened patients;
- Screen failure patients and reasons for screen failure;
- Non-randomized but treated patients;
- Randomized patients;
- Randomized but not treated patients and reason for not treated (not applicable for patients randomized to usual care arm without intent to prescribe an additional LMT);
- Randomized and treated patients;
- Patients who completed the study treatment period as per protocol;
- Patients who discontinued the study treatment and main reason for permanent treatment discontinuation (not applicable for patients randomized to usual care arm without intent to prescribe an additional LMT);
- Patients who completed the study period as per protocol;
- Patients who discontinued the study and main reason for study discontinuation;
- Status at last study contact.

For all categories of patients (except for the screened and non-randomized categories) percentages will be calculated using the number of randomized patients as the denominator.

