### Stratification

A shift table on randomized patients will describe the strata recorded in IVRS (no additional LMT, or intent to initiate fenofibrate, ezetimibe, omega-3 fatty acids, or nicotinic acid) and the actual LMT received recorded in the e-CRF on the UC medication page. A listing of patients with discrepancies between strata will be provided.

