#### 2.2.1 Randomization and drug dispensing irregularities

Randomization and drug-dispensing irregularities occur whenever:

1. A randomization is not in accordance with the protocol-defined randomization method, such as a) an ineligible patient is randomized, b) a patient is randomized based on an incorrect stratum, c) a patient is randomized twice, or d) in a dynamic randomization scheme the treatment assignment is, in fact, not random, due to a computer program error.

OR

2. A patient is dispensed an alirocumab kit/ usual care package (e.g., blister packs, pill container) not allocated by the protocol-defined randomization, such as a) a patient at any time in the study is dispensed a different treatment kit/package than as randomized (which

26-Apr-2017

Version number: Final

26-Apr-2017

may or may not contain the correct-as-randomized IMP), or b) a nonrandomized patient is treated with IMP reserved for randomized patients.

Randomization and drug-dispensing irregularities will be monitored throughout the study and reviewed on an ongoing basis. Randomization irregularities are recorded in the IVRS/IWRS. Drug dispensing irregularities come from IVRS/IWRS only for the alirocumab arm, as the process of drug supply for usual care is not handled by IVRS/IWRS and is site-specific. Therefore drug dispensing irregularities presented in this section will only concern the alirocumab arm. The corresponding information for usual care would be found in the CSR as qualitative deviations in the specific section.

Randomization and drug-dispensing irregularities to be prospectively identified include but are not limited to:

Randomization irregularities (both treatment arms)	Drug dispensation irregularities (alirocumab)	
Randomization by error	Alirocumab kit dispensation without IVRS transaction	
Patient randomized twice	Erroneous alirocumab kit dispensation	
Stratification error	Alirocumab kit not available	
	An alirocumab kit allocated at Day 1 or any unscheduled replacement before Week 12 is administered to the patient after his up-titration visit (Week 12)	

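### Minor: the re-run labelled as a check on stratum-entry mistakes codes the stratum from the usual-care drug taken after randomisation, in one arm only, so it cannot show robustness to those mistakes

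*SAP*

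**What the plan says.** The primary MMRM (SAP 2.4.4.1.1) uses the stratum recorded in IVRS. Under SAP 2.4.4.1.3 the model is re-run to assess "robustness of the primary analysis to randomization stratum mistakes", a mistake being an IVRS stratum that differs from the actual one. The actual stratum, taken from the e-CRF, "is defined, for the patients randomized to usual care only, as the actual usual care treatment taken for the longer time". A fallback sentence, which begins "In case no additional LMT is recorded using e-CRF page" and names the usual-care medication page, places the patient in the stratum with no intent to add a lipid-modifying therapy (LMT). Forest plots show the sensitivity analyses together with the main result.

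The stratification factor is defined in SAP 1.1 as the investigator's "selection of usual care therapy prior to randomization (5 strata: no additional lipid modifying therapy [LMT" and so on through the four drugs. SAP 1.4 says that, for a patient randomised to alirocumab, "the Investigator will not institute the LMT option that was selected and entered into IVRS but instead treat the patient with open-label alirocumab". A usual-care patient is started on the option entered in IVRS.

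Three other places bear on the point:
- SAP 2.2 has a disposition category for "Randomized but not treated patients and reason for not treated".
- SAP 2.2 (Stratification) plans a shift table of IVRS strata against "the actual LMT received recorded in the e-CRF on the UC medication page".
- SAP 2.2.1 lists stratification error under "Randomization irregularities (both treatment arms".

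**The concern.** A stratum-entry mistake is a mismatch between what was keyed into IVRS and what the investigator intended before randomisation. The re-run compares the IVRS entry with what the patient took afterwards. These are different things. The second is also a post-randomisation variable, and it is brought into the model in one arm only.

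What is at stake is interpretation. The result sits beside the primary estimate as a robustness check. Close agreement would be read as evidence that entry mistakes do not matter, and a gap as evidence that they do. The definition supports neither reading.

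**Working it through.** **1. What the rule does to each kind of patient**

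| Patient | IVRS entry | Stratum in the re-run |
|---|---|---|
| Usual care, never starts the drug, nothing on the page | right | changed to no intent |
| Usual care, another option taken for longer | right | changed to that option |
| Usual care, stops the one chosen drug early | right | unchanged |
| Usual care, wrong entry that the site follows | wrong | unchanged, so missed |
| Usual care, wrong entry, intended drug given | wrong | corrected |
| Alirocumab, any entry | right or wrong | no drug to derive it from; IVRS value on the natural reading |

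Only one kind of genuine error is repaired, and two kinds of correct entry are altered. The first row is a case that SAP 2.2 provides for. The second is possible because Protocol 8.8.1 lets the investigator modify LMT, for example after a confirmed triglyceride alert.

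**2. Where the errors are expected to lie**

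The option is entered before 2:1 randomisation, so errors should divide as the arms do: 280/420 = 66.7% under alirocumab. The documents give no error rate. At assumed rates of 2%, 5% and 10%:
- all entries: 420 × rate = 8.4, 21 and 42 errors
- alirocumab arm: 280 × rate = 5.6, 14 and 28 errors

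**3. Size of the shift when every entry is correct**

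The plan has no figure to reproduce. The sample-size text is not shown, and no stratum shares, effects or non-start rates are given. All inputs below are therefore assumptions, and alirocumab patients keep the IVRS stratum.

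In a model with treatment and stratum, the treatment estimate is Σw·d / Σw over strata. Here d is the within-stratum difference and w = n(alirocumab) × n(usual care) / (their sum).

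An illustration collapses the strata to two. Assume 45% no LMT, usual-care means of 0 without LMT and −20 on LMT, alirocumab −35 in both strata, and 20% of LMT patients never starting, with mean 0.
- Usual care by IVRS: 63 no LMT and 77 LMT, of whom 15.4 never start. The LMT mean is 0.8 × (−20) = −16. Differences are −35 and −19.
- Primary coding, with weights proportional to 63 and 77: (−35 × 63 − 19 × 77)/140 = −26.2.
- Re-run coding: 63 + 15.4 = 78.4 no LMT (mean 0) and 61.6 LMT (mean −20). Differences are −35 and −15. Weights are 126 × 78.4/204.4 = 48.33 and 154 × 61.6/215.6 = 44.00.
- Re-run estimate: (−35 × 48.33 − 15 × 44.00)/92.33 = −25.5, a shift of about +0.7 with no entry wrong.

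A wider grid used the same least-squares logic in 135 scenarios per rate: three sets of shares (no LMT 30%, 45% or 60%), three sets of usual-care effects (0 to −20), five prognosis sets (0 to ±10), alirocumab −35, and never-starter outcome −3, 0 or +5. The treatment difference was about −26 to −34. The last column is a repeated-measures check in four of the scenarios, with baseline, four visits, stratum-by-time terms and 12% dropout.

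| Never start | Shift, grid | Shift, MMRM check |
|---|---|---|
| 0% | 0.00 | not run |
| 5% | −0.11 to +0.32 | −0.01 to +0.31 |
| 10% | −0.21 to +0.66 | +0.02 to +0.66 |
| 20% | −0.39 to +1.33 | +0.07 to +1.32 |

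For comparison, SE = SD × √(1/280 + 1/140) = SD × 0.1035, which is 2.1 at SD 20 and 3.1 at SD 30. In the scenario with the largest shift, at 20% and n = 420 (300 runs), the mean shift was +1.31 (95% range 0.41 to 2.33), and the primary estimate had SD 2.8.

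A separate simulation (2,000 trials per rate) used a Week 24 ANCOVA; shares 35/20/30/13/2% for none, fenofibrate, ezetimibe, omega-3 and nicotinic acid; usual-care means 0/−8/−18/−4/−10; alirocumab −35; SD 30. Usual-care LMT patients with poorer outcomes were the more likely to switch or not start.

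| Switch or never start | Correct entries re-coded | Primary coding | Re-run | Shift |
|---|---|---|---|---|
| 5% | 4.6 | −27.21 | −27.12 | +0.09 |
| 10% | 9.1 | −27.40 | −27.20 | +0.20 |
| 20% | 18.2 | −27.23 | −26.79 | +0.44 |

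The SE was about 3.1 throughout.

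**4. Genuine errors**

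With 2% to 10% of entries wrong in both arms, correcting both arms shifts the estimate by 0.00. Correcting usual care only shifts it by −0.57 to +0.51. This assumes that the drug taken reveals the true intention, which favours the SAP's rule.

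**The case against.** **The proxy is reasonable.** A usual-care patient treated per protocol receives the option selected, so the drug taken stands in for the intention, and using the longest-taken drug limits the influence of brief switches. This holds for compliant patients with correct entries, who need no correction. The proxy fails where it is needed: the site starts what was entered, so a wrong entry that is followed looks right.

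**Non-start may be rare.** Usual-care treatment should start within 7 days (Protocol 6.1), and the strategy is meant to stay unchanged (Protocol 4, rationale for design). A never-starter matters only if lipid values exist in the Week 8 to 24 windows. The documents do not say whether a prescribed but unstarted drug would appear on the page. All this stands: the 5% to 20% rates are assumptions, and the disposition category shows only that the case is foreseen.

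**Other checks exist.** The SAP states openly that the definition is for usual care only, and stratification errors are logged and reported for both arms under 2.2.1. So the inability to detect alirocumab errors is a property of this re-run, not of the whole plan. But the log is not fed into the model, and the shift table relies on the usual-care medication page.

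**A stronger reading that does not hold.** A reader might infer that the fallback sentence, which names no arm, moves every alirocumab patient into the no-intent stratum and so changes the comparison drastically. The context does not support this. The sentence continues a definition limited to usual care, and SAP 2.4.3 identifies the page it names as the source for the usual-care arm. With no e-CRF stratum defined for alirocumab, the IVRS value is the natural one to keep. What remains is that the SAP does not say so.

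**Conclusion.** The point is minor, but the rule is wrong as written. The re-run adjusts for treatment received after randomisation in one arm and presents this as a test of entry mistakes. Agreement with the primary analysis does not show robustness to stratum errors, about two thirds of which are expected where the re-run cannot correct them. A gap can arise with every entry correct.

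The numerical effect is small. With alirocumab patients in the IVRS stratum, the expected shift stays below one standard error even at an assumed 20% non-start. That rests on assumed shares, effects, prognosis and SD, since the documents supply none of them.

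It should not be inferred that the efficacy conclusion is at risk. The primary MMRM and the pattern-mixture analysis use the IVRS stratum, and the testing hierarchy does not depend on this re-run. The harm is confined to a mislabelled robustness check.

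**What to change.** In SAP 2.4.4.1.3, define the corrected stratum in both arms as the option intended before randomisation. Change the IVRS value only for stratification errors documented under SAP 2.2.1 where that intended option is recorded. Otherwise keep the IVRS stratum, and state this explicitly for alirocumab patients. Report how many entries were changed; if there are so few that the re-run nearly equals the primary analysis, say so.

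If a re-run by usual-care drug actually taken is still wanted, keep it under its own label as an analysis by treatment received, not as a check on stratum mistakes.

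The cost is a few sentences of SAP text and a few lines of programming, with no new data. The documents do not say whether the intended option is recorded for each logged error; where it is not, the IVRS stratum stays.
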